15.2.1.4. Proportion of subjects who achieve a SAPS-PD response

SAPS-PD response is defined as a 30%, 50% and 100% or greater improvement (i.e. decrease) in SAPS-PD total score from Baseline.

The percent change in SAPS-PD total score from Baseline will be calculated by:

$$\frac{\text{SAPS-PD total score at a visit or the LOCF endpoint} - \text{SAPS-PD total score at Baseline}}{\text{SAPS-PD total score at Baseline}} \times 100\%$$

For each subject, the responder indicator will be set to 1 if the percent change is $\leq -30\%$. The indicator will be set to 0 if the percentage is $> -30\%$. The indicator will be set to missing if the percentage is missing.

In addition, SAPS-PD response defined by a series of additional thresholds will be assessed; that is, having a 50% or greater and 100% or greater improvement in SAPS-PD total score from Baseline.

SAPS-PD response at all three thresholds will be derived for all post-baseline time points during the double-blind period.

15.2.1.5. Subjects with SAPS-PD percent change from baseline

The proportion of subjects achieving a given SAPS-PD percent change from baseline or lower at the Week 6 LOCF endpoint will be calculated for each treatment group. This calculation will be performed at multiple levels of percent change from baseline, from -100% to $\geq 100\%$, with 5% increments. The results will be reported in a graph with the percent change from baseline threshold on the x-axis and proportion of subjects in each treatment group on the y-axis.

15.2.2. MISSING DATA METHODS FOR SECONDARY EFFICACY VARIABLE(S)

For rating scales with more than one item, if any item score contributing to the total score or individual domain score is missing, then the total score or individual domain score will be set to missing. The change from baseline scores will also be set to missing accordingly.

Document:

\

Author:

Version Number:
Version Date:

Final 1.0
24FEB2020

Template No: CS_TP_BS016 Revision 4
Effective Date: 01Apr2016

Reference: CS_WI_BS005

The MMRM analysis of the continuous secondary efficacy variables will be based on observed data (with early termination data mapped as described in Section 6.4). Missing data will not be imputed. SAPS-PD responder calculation will be based on the SAPS-PD total score at the Week 6 LOCF endpoint.

The ANCOVA analyses of the continuous secondary efficacy variables will utilize the change from baseline at the Week 6 LOCF endpoint, as a sensitivity analysis. Refer to section 6.3 for further details on LOCF imputation.

15.2.3. ANALYSIS OF SECONDARY EFFICACY VARIABLES

15.2.3.1. Analysis of change from baseline in CGI-S score at Week 6 during the DB period

Change from baseline in CGI-S score at Week 6 will be analyzed using an MMRM model similar to the model used in the primary analysis of the primary efficacy variable (see Section 15.1.3), with baseline CGI-S score as a covariate. Only subjects on-period data will be taken into account in this analysis (see Section 6.9).

Relationships between CGI change and SAPS-PD will be explored.

15.2.3.2. Analysis of change from baseline in NPI score and NPI (H+D) score at Week 6 during the DB period

Change from baseline in NPI score at Week 6 will be analyzed using an MMRM model similar to the model used in the primary analysis of the primary efficacy variable (see Section 15.1.3), with baseline NPI score as a covariate. Only subjects on-period data will be taken into account in this analysis (see Section 6.9). These summaries on NPI will be repeated on NPI (H+D).

Relationships between NPI and NPI (H+D) changes and SAPS-PD will be explored.

15.2.3.3. Analysis of change from baseline in MMSE score at Week 6 during the DB period

Change from baseline in MMSE score at Week 6 will be analyzed using an MMRM model similar to the model used in the primary analysis of the primary efficacy variable (see Section 16.1.3), with baseline MMSE score as a covariate (>24 or <= 24). Only subjects on-period data will be taken into account in this analysis (see Section 6.9)

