15.3.5.2. Secondary Efficacy Endpoint Analysis

CGI-S score

Change from Baseline in CGI-S score at Week 6 during the DB period will be analyzed using an MMRM model similar to that of the primary efficacy variable, with change from Baseline in CGI-S score at each visit as the response variable and Baseline CGI-S score as a covariate.

NPI

Change from Baseline in NPI score at Week 6 during the DB period will be analyzed using an MMRM model similar to that of the primary efficacy variable, with change from Baseline in NPI score at each visit as the response variable and Baseline NPI score as a covariate.

MMSE

Change from Baseline in MMSE score at Week 6 during the DB period will be analyzed using an MMRM model similar to that of the primary efficacy variable, with change from Baseline in MMSE score at each visit as the response variable and Baseline MMSE score as a covariate.

The absolute values of the secondary efficacy measures at both the DB baseline and OL baseline, and at each scheduled post-baseline extension visit, will be summarized descriptively. Changes from baseline in these measures will be summarized at each scheduled post-baseline extension visit, based on both the DB baseline and the OL baseline.

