3.7. CHANGES TO ANALYSIS FROM PROTOCOL

There is no change in the analysis from protocol.

Document:

\

Author:

Version Number:

Final 1.0

Version Date:

24FEB2020

Template No: CS_TP_BS016 Revision 4
Effective Date: 01Apr2016

Reference: CS_WI_BS005

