7. STATISTICAL CONSIDERATIONS

7.1. ADJUSTMENTS FOR COVARIATES AND FACTORS TO BE INCLUDED IN ANALYSES

The following covariates are used in the analyses. For details of their inclusion in the models, see specific analysis sections.

- Baseline value of the variable to be analyzed

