7.5. EXAMINATION OF SUBGROUPS

Subgroup analyses will be conducted as stated in the respective efficacy and safety analysis sections. It should be noted that the study was not powered to detect treatment differences within subgroups.

The following subgroups will be assessed:

- Sex:
 - Female
 - Male
- Age group (years):
 - >=55 to <65
 - >=65 to <75
 - >=75
- Number of prior hospitalizations for PDP:
 - 0
 - 1
 - 2
 - 3 or more
- Duration of PDP (years):
 - < 5
 - >= 5 to < 10
 - >= 10 to < 20
 - >= 20
- Baseline MMSE (categories for subgroup analysis are different than subgroups presented for the demographic summaries, see Section 10):
 - >24
 - <=24

Document:

\

Author:

Version Number:

Final 1.0

Version Date:

24FEB2020

Template No: CS_TP_BS016 Revision 4
Effective Date: 01Apr2016

Reference: CS_WI_BS005

- Baseline NPI Hallucinations + Delusions (NPI [H+D]) Severity:
 - ≥ 6 to < 12
 - ≥ 12
- Lead-in Status:
 - Lead-in
 - Non Lead-in

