15.1.4.4. Analysis of covariance

As another supportive analysis for the efficacy endpoints of change from Baseline in SAPS-PD total score at Week 6, missing data at Week 6 will be imputed using the last observation carried forward (LOCF) method, and the data will be analyzed using an ANCOVA model. The response variable for the model will be: change from Baseline in SAPS-PD total score at the Week 6 LOCF endpoint. The ANCOVA model will include treatment as fixed factors and include Baseline score as a covariate.

The proportion of subjects by percent change from baseline at the LOCF Endpoint will be plotted by treatment group.

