15.2.4. SENSITIVITY ANALYSIS OF SECONDARY EFFICACY VARIABLES

Sensitivity analyses of CGI-S score will be performed similarly to those outlined in Section 15.1.4.

Sensitivity analyses of NPI and MMSE score will be performed using the ANCOVA model described in Section 15.1.4.4.

Document:

\

Author:

Version Number:

Final 1.0

Version Date:

24FEB2020

Template No: CS_TP_BS016 Revision 4
Effective Date: 01Apr2016

Reference: CS_WI_BS005

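### SAP 15.2.3.3 attaches a two-level cut at 24 to the baseline covariate of the MMSE model; the protocol has no cut and SAP 3.7 declares no change

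*SAP*

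**What the plan says.** Protocol 15.3.5.2 describes the MMSE analysis as an MMRM like the primary one, "with change from Baseline in MMSE score at each visit as the response variable and Baseline MMSE score as a covariate". It mentions no categories.

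SAP 15.2.3.3 describes the same analysis, but "with baseline MMSE score as a covariate (>24 or <= 24", so a cut at 24 follows the word score. SAP 3.7 says: "There is no change in the analysis from protocol".

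Other places in the SAP bear on the form of this covariate:

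- SAP 15.2.3.1 fits CGI-S "with baseline CGI-S score as a covariate", and 15.2.3.2 treats NPI in the same way. Neither has a cut.
- SAP 15.1.3, the primary model, uses the baseline SAPS-PD total score as a covariate. In the Appendix 3 code the CLASS statement lists only subject, treatment and visit, so baseline enters as a continuous term.
- SAP 15.2.4: "Sensitivity analyses of NPI and MMSE score will be performed using the ANCOVA model described in Section 15.1.4.4". That section, 15.1.4.4, says: "The ANCOVA model will include treatment as fixed factors and include Baseline score as a covariate".
- SAP 7.1 lists one covariate, "Baseline value of the variable to be analyzed", and refers to the individual analysis sections for how it enters each model.
- SAP 7.5 uses the same two levels as a subgroup factor: "Baseline MMSE (categories for subgroup analysis are different than subgroups presented for the demographic summaries, see Section 10".

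**The concern.** The sentence in SAP 15.2.3.3 can be programmed in two ways. One programmer reads score and fits a continuous covariate. Another reads the parenthesis and fits a two-level term. The two models give different estimates and standard errors for one of the three secondary endpoints, and the second departs from the protocol without being declared. Settling such choices before unblinding is the purpose of a SAP.

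The literal reading has two further costs. It discards the baseline information within each category, in a trial of about 36 subjects. It also adds a difference in covariate form between the main MMSE analysis and its sensitivity ANCOVA. Those two already differ in model and in the use of LOCF, so a gap between their results would be harder to interpret.

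**Working it through.** **Text comparison.** Every description of a baseline adjustment for MMSE, and for the outcomes modelled in parallel, uses the undivided score, except the parenthesis in SAP 15.2.3.3. Elsewhere the cut at 24 appears only as the SAP 7.5 subgroup factor. The efficacy subgroup analyses apply that factor to SAPS-PD (15.1.5) and CGI-S (15.2.5). No MMSE subgroup analysis is planned.

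**Plan figures.** The documents give no precision or power figure for MMSE. The only power statement (Protocol 15.1, SAP 3.4) concerns SAPS-PD by a two-sample t-test without covariates. With 24 versus 12 subjects, the noncentral t (34 degrees of freedom) gives 59.4%, 48.6%, 37.8% and 28.0%, against the stated 59%, 48%, 37% and 27%. It is reproduced to within about one point and does not bear on the covariate.

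**Size of the loss if the split is followed.** Only the entry range comes from the documents: a baseline MMSE above 16 out of 30 (Protocol 8.1, criterion 7), so integers 17 to 30. The rest is assumed:

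- baseline roughly normal on 17 to 30, with mean 23, 24 or 25 and SD 3 or 4 before truncation;
- r, the correlation between baseline and Week 6, from 0.5 to 0.9;
- k, the Week 6 SD divided by the baseline SD, from 0.9 to 1.2.

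The slope of change on baseline, in baseline units, is rk − 1. With the score fitted, the residual variance is k²(1 − r²) times the baseline variance. With the split, the part (rk − 1)²W is added, where W is the fraction of baseline variance left within the two categories. Hence

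SE ratio (split / score) = √[1 + (rk − 1)² W / (k²(1 − r²))].

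Under the assumed distributions, 45% to 69% of subjects fall at or below 24 and W runs from 0.308 to 0.388. Examples at W = 0.388:

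- k = 1, r = 0.5: 0.25 / 0.75 = 0.333; × 0.388 = 0.129; √1.129 = 1.063, so 6.3% larger.
- k = 1, r = 0.9: 0.01 / 0.19 = 0.0526; × 0.388 = 0.0204; √1.0204 = 1.010, so 1.0% larger.
- k = 0.9, r = 0.5: 0.3025 / 0.6075 = 0.498; × 0.388 = 0.193; √1.193 = 1.092, so 9.2% larger.

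Excess standard error in per cent, over the range of W:

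| k | r = 0.5 | r = 0.8 | r = 0.9 |
|---|---|---|---|
| 0.9 | 7.4–9.2 | 4.1–5.1 | 3.6–4.5 |
| 1.0 | 5.0–6.3 | 1.7–2.1 | 0.8–1.0 |
| 1.1 | 3.4–4.2 | 0.5–0.6 | 0.0 |
| 1.2 | 2.3–2.8 | 0.1 | 0.4–0.5 |

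The loss vanishes where rk is close to 1, because change then hardly depends on baseline.

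The entry floor of 17 does not apply at Week 6, which tends to push k above 1. With equal SDs before truncation and no ceiling effect at Week 6, k is 1.01 to 1.18 and the excess is 0.5% to 5.5%. A ceiling at 30 could pull k back down, so values below 1 are not excluded.

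**Simulation check.** The MMRM was simulated with two post-baseline visits (Visits 5 and 7), unstructured covariance, 24 versus 12 subjects and complete data. It used a residual correlation of 0.5 between visits, model standard errors without the Kenward-Roger correction, and 2,000 trials per setting. Over two of the baseline distributions the mean SE ratios were 1.076 to 1.095 (r = 0.5, k = 0.9), 1.050 to 1.061 (0.5, 1.0), 1.018 to 1.022 (0.8, 1.0) and 1.008 to 1.010 (0.9, 1.0), in line with the formula. With a true effect of zero, the mean estimate under the split was within 0.05 of zero and within 0.01 of the score-based estimate from the same trials (Monte Carlo error about 0.02).

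**The case against.** The best defence is that this is a slip of wording. The sentence says score, the model is to be similar to the primary one, and the primary model in 15.1.3 uses the word factors for its categorical terms. A sensible programmer might ignore the parenthesis, and then nothing is lost. That may be so, but nothing in the documents settles it, and a programmer who follows the text literally has support for the split.

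Several stronger readings are tempting and should not be drawn:

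- **That SAP 7.1 contradicts 15.2.3.3.** It leaves the form of inclusion to the analysis sections, and a categorised baseline is still a form of the listed covariate. It supports the point without creating a conflict.
- **That the sensitivity ANCOVA contradicts it.** SAP 15.1.4.4 was written for SAPS-PD and speaks generically of the baseline score. This is an inconsistency between two analyses, not a contradiction. The real conflict is Protocol 15.3.5.2 and SAP 3.7 against 15.2.3.3.
- **That the cut was carried over from SAP 7.5, or that the split is deliberate.** The values match the subgroup cut, but no document states the origin or the intent.
- **That the same sentence's reference to Section 16.1.3, instead of 15.1.3, is evidence about the parenthesis.** Similar misnumbered references occur in SAP 7.3 and 14.1. They are clerical and add no weight.
- **That the loss could be far larger.** Residual variance up to 44% higher, or √1.44 = 1.20 in standard error, needs a correlation of 0.7 in absolute value between baseline and change. With equal SDs that correlation is −√((1 − r)/2), so 0.7 requires r = 1 − 2 × 0.49 = 0.02: baseline and Week 6 MMSE almost unrelated. The documents give no ground for that.
- **That the comparison is biased.** Treatment is randomised, and the simulation found no bias with complete data. Dropout that depends on baseline differently by arm could leave a little. A single-visit check with about 15% such dropout found at most about 0.06 points.

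**Conclusion.** The conflict stands in the text and needs no assumption: the protocol takes the baseline MMSE score, the SAP adds a two-level cut for MMSE alone, and the SAP declares no change. Followed literally, this is an undeclared and generally less precise model.

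Its size rests wholly on assumed MMSE distributions and correlations: a standard error about 0% to 9% larger over the whole grid. The upper end needs a Week 6 SD below the baseline SD together with a correlation of 0.5.

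The reach is limited to one secondary endpoint in an exploratory trial, with nominal p-values under SAP 7.4. Severity: minor.

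**What to change.** Before unblinding, delete the parenthesis with the cut at 24 from SAP 15.2.3.3 and state that baseline MMSE score enters as a continuous covariate, as for SAPS-PD, CGI-S and NPI. Keep the cut only for the SAP 7.5 subgroups. If the split is intended, declare and justify it in SAP 3.7 and say which form the sensitivity ANCOVA uses.

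As a separate editorial change, correct the reference in the same sentence from Section 16.1.3 to 15.1.3.

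The cost is one deletion and one corrected reference. No new data or analyses are needed.

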15.2.4. SENSITIVITY ANALYSIS OF SECONDARY EFFICACY VARIABLES

Sensitivity analyses of CGI-S score will be performed similarly to those outlined in Section 15.1.4.

Sensitivity analyses of NPI and MMSE score will be performed using the ANCOVA model described in Section 15.1.4.4.

Document:

\

Author:

Version Number:

Final 1.0

Version Date:

24FEB2020

Template No: CS_TP_BS016 Revision 4
Effective Date: 01Apr2016

Reference: CS_WI_BS005

15.2.5. SUBGROUP ANALYSIS OF SECONDARY EFFICACY VARIABLE(S)

Subgroup analysis of CGI-S score will be performed similarly to those described in Section 15.1.5.

15.2.6. ANALYSIS OF SASPS-PD RESPONDER

SAPS-PD response will be analyzed using a logistic regression model with responder indicator as the dependent variable and treatment as categorical factors and baseline SAPS-PD total score as a covariate. The analysis will be performed at the Week 6 LOCF endpoint as well as for each of the post-baseline scheduled visits during the double-blind period.

Odds ratio and its 95% CI as estimated by the model will be presented. In addition, the Number Needed to Treat (NNT) will be calculated for SEP-363856 group as:

$$NNT = \frac{1}{\text{Risk Reduction (RR)}} = \frac{1}{\text{SAPS-PD Response Rate}_{\text{SEP-363856}} - \text{SAPS-PD Response Rate}_{\text{Placebo}}}$$

The 95% CI of NNT will be obtained by taking the reciprocal of the 95% CI bounds of the Absolute Risk Reduction when both lower and upper confidence limits are positive. The NNT and its 95% CI will be provided as integers; any fractional values will be rounded up to the nearest integer (the lower confidence limit will be rounded down and the upper confidence limit will be rounded up)

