3.4. DETERMINATION OF SAMPLE SIZE

A total of approximately 36 subjects will be randomized in 2:1 ratio to SEP-363856 and placebo, with approximately 24 subjects assigned to SEP-363856 and 12 subjects assigned to placebo. The sample size will provide powers of 59%, 48%, 37%, and 27% to detect treatment effect sizes of 0.8, 0.7, 0.6, and 0.5, respectively, in change from Baseline in SAPS-PD at Week 6 for SEP-363856 versus placebo. It was estimated by using a two independent sample t-test method with 2-sided significant level of 0.05. The sample size was determined for the purposes of exploring the efficacy, safety and tolerability of flexible dosing with SEP-363856 (25, 50, or 75 mg/day) for 6 weeks in male and female subjects with a clinical diagnosis of PDP. A sufficient number of subjects will be enrolled to ensure 36 randomized subjects.

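### The responder logistic regression has no rule for an arm with zero responders, a case that is plausible at the 100% threshold with about 12 placebo subjects

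*SAP*

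**What the plan says.** SAP 15.2.1.4: "SAPS-PD response is defined as a 30%, 50% and 100% or greater improvement (i.e. decrease) in SAPS-PD total score from Baseline". The same section derives all three thresholds at every post-baseline time point of the double-blind period.

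SAP 15.2.6: "SAPS-PD response will be analyzed using a logistic regression model with responder indicator as the dependent variable". The model has treatment as a factor and baseline SAPS-PD total score as a covariate. On timing: "The analysis will be performed at the Week 6 LOCF endpoint as well as for each of the post-baseline scheduled visits". The scheduled SAPS-PD visits are Weeks 2, 3, 5 and 6 (SAP 15.1.3), so with the LOCF endpoint there are five time points. On output: "Odds ratio and its 95% CI as estimated by the model will be presented". An NNT is also planned. Its interval is the reciprocal of the risk-difference limits, given only when both limits are positive, and the risk-difference method is not named.

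SAP 3.4 plans "approximately 24 subjects assigned to SEP-363856 and 12 subjects assigned to placebo".

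No penalised or exact method, and no rule for separation or empty cells, is given for this model. The convergence fallback in SAP 15.1.3 covers only the MMRM covariance structure. The code in SAP Appendix 3 covers only the MMRM and the two imputation analyses.

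**The concern.** The SAPS-PD total runs from 0 to 45 (SAP 15.1.1), so a 100% response requires a score of exactly 0. With about 12 placebo subjects, an arm without a single responder is a realistic possibility. The maximum-likelihood estimate of the treatment log-odds ratio then has no finite value, and a Wald interval around it has no meaning. If neither arm has a responder, there is nothing to fit.

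The SAP promises an odds ratio and interval for each analysis, so the team would have to choose a remedy after seeing the data. A second effect is easier to miss. An empty placebo cell also makes the estimated placebo variance zero, which narrows a Wald interval for the risk difference and can produce a favourable-looking NNT interval.

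**Working it through.** **Plan's own figure.** The documents give no figure for the responder analysis. The only sample-size statement is "powers of 59%, 48%, 37%, and 27% to detect treatment effect sizes of 0.8, 0.7, 0.6, and 0.5", from a "two independent sample t-test method with 2-sided significant level of 0.05". With 24 and 12 subjects, 34 degrees of freedom and noncentrality d × √(24 × 12 / 36), the noncentral t gives 59.4%, 48.6%, 37.8% and 28.0%. This agrees within about one point and confirms the arm sizes used below.

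**Inputs.** Arm sizes 12 and 24 are from SAP 3.4. The response rates are assumptions.

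**Zero placebo responders in one analysis:** (1 − p)^12.

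| Assumed placebo rate | Chance of 0 of 12 |
|---|---|
| 5% | 0.95^12 = 0.540 |
| 10% | 0.90^12 = 0.282 |
| 15% | 0.85^12 = 0.142 |
| 20% | 0.80^12 = 0.069 |
| 30% | 0.70^12 = 0.014 |

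The chance exceeds one half only below 1 − 0.5^(1/12) = 5.6%, and drops under 10% only above 1 − 0.1^(1/12) = 17.5%. By-visit denominators can be smaller than 12, because off-period assessments count as missing (SAP 6.9). With 10 evaluable placebo subjects the chance is 60% at a 5% rate and 35% at 10%.

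**Zero responders in at least one arm:** a + b − ab, with a = (1 − p_placebo)^12 and b = (1 − p_active)^24.

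- 5% and 5%: 0.5404 + 0.2920 − 0.1578 = 0.675; both arms empty 0.158
- 5% and 10%: 0.577; both arms empty 0.043
- 10% and 10%: 0.340; both arms empty 0.023
- 10% and 20%: 0.286; both arms empty 0.001
- 20% and 30%: 0.069

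The baseline covariate can in principle cause separation too. In a simulation (1,500 runs per setting, assumed slope −0.7 on the log-odds scale per SD), it added at most 0.5 percentage points to the zero-cell frequency.

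**What a remedy gives, 0/12 placebo against 4/24 active.** The maximum-likelihood odds ratio is infinite. Adding 0.5 to each cell, which equals Firth's method without the covariate, gives (4.5 × 12.5) / (20.5 × 0.5) = 5.49. The standard error of the log is √(1/4.5 + 1/20.5 + 1/0.5 + 1/12.5) = 1.533, so the Wald 95% interval is 0.27 to 110.8. Fisher's exact p is 0.278.

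**Both arms empty.** The same correction gives (0.5/24.5) / (0.5/12.5) = 0.51. This apparent advantage for placebo comes only from the 2:1 allocation.

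**NNT, same 0/12 against 4/24.** The risk difference is 0.167. Its Wald standard error is √(0.1667 × 0.8333 / 24 + 0) = 0.0761, giving 0.018 to 0.316. Both limits are positive, so the SAP rule would print an NNT interval of 3 to 57. The Newcombe interval is −0.10 to 0.36, for which the rule prints no NNT interval.

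**The case against.** Four points can be made for leaving the plan alone.

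1. *No rate is given.* A reader might infer that a zero cell is likely in this trial. The documents do not support that without a condition: at an assumed 20% placebo rate the chance is about 7%. Low early rates are plausible. Entry requires psychosis severe enough to warrant antipsychotics (Protocol 8.1), and the first post-baseline rating is at Day 8. But no visit-level rate is stated. This objection stands, so the figures are only a range.

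2. *Maximum likelihood and Wald are not named.* A reader might infer that the SAP prescribes them. It says only that a logistic model supplies the estimate and interval. The unpenalised fit is the natural default, and it remains an inference. The firm statement is that the method is unspecified.

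3. *The model might apply at 30% only.* SAP 15.2.1.4 codes the responder indicator explicitly at 30% and then says that further thresholds will be assessed, namely "having a 50% or greater and 100% or greater improvement in SAPS-PD total score from Baseline". If only the 30% indicator were modelled, the problem would largely vanish (1.4% at an assumed 30% placebo rate). However, the opening definition of response lists all three thresholds, and SAP 15.2.6 models response without restriction. The wider reading is the better one.

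4. *Little depends on it.* Response is not among the secondary endpoints in Protocol 6.2, p-values are nominal (SAP 7.4), and an infinite odds ratio is visibly not an estimate. SAP 15.2.1.5 already plots the proportion reaching each level of change, starting at −100%, at the Week 6 LOCF endpoint. This stands and sets the low priority. It does not cover the NNT interval, which could look credible and be wrong.

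**Conclusion.** The gap is real and minor. The SAP commits to an odds ratio and interval at three thresholds and five time points, with about 12 placebo subjects and no rule for an empty cell. At the 100% threshold the chance of no placebo responder, per analysis, runs from 54% at an assumed 5% rate to 7% at 20%. Since that threshold is analysed five times, the chance of at least one such analysis is no smaller than the largest single value.

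This rests on the assumed rates, on the planned arm sizes, on reading SAP 15.2.6 as covering all thresholds, and on a default fit. A reader might go further and infer that the efficacy conclusion is at risk. It is not: the primary analysis is an MMRM of the change in total score and does not use this model. Moderate response rates at the 30% threshold would make empty cells rare there. The point is a cheap improvement.

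**What to change.** Add to SAP 15.2.6, before unblinding:

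- When either arm has no responders, or all its subjects respond, the odds ratio comes from Firth's penalised likelihood with a profile-likelihood interval (FIRTH and CLODDS=PL in PROC LOGISTIC). Using Firth for all responder models is also acceptable and simpler to state.
- When neither arm has a responder, report counts only, with no odds ratio.
- Report the risk difference at every threshold with a Newcombe (or exact) interval, and derive the NNT interval from it.
- State that the model is fitted at all three thresholds.

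The cost is a few sentences and two SAS options. The downside is some shrinkage of the odds ratio. Intervals become finite but stay very wide, as the 0.27 to 111 example shows, so at the 100% threshold the counts and risk difference will carry most of the information.
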